Full study protocol and statistical analysis plan

Official Title of the study:

Cognitive progressive muscular relaxation therapy on couples undergoing IVF-ET

Date of the document:

20th April 2019

Contents:

- 1. Participant Flow
- 2. Baseline Characteristics
- 3. Outcome Measures
- 4. Adverse Event Information
- 5. Limitations and Caveats
- 6. Certain Agreements
- 7. Results Point of Contact

1. Participant Flow

Recruitment Details

We will choose Infertility Reproductive Center, Second Xiangya Hospital, Central South University to recruit the participants. The recruitment will start at May 1st 2019. The recruitment announcement will be distributed to the participants via notice board in the department.

Pre-assignment Details [*]

We firstly will assess the recruited people to ensure meeting the inclusion and exclusion criteria. Then the final enrolled participants can be sure and randomized assignment will be conducted.

Enrollment (total, anticipatory)	138			Record the number of the eligible and the excluded
Allocation (randomized)	Group A	Group B	Group C	Record the number of the received and the unreceived
	46	46	46	
Follow-up (immediately after intervention)				Record the number of the received and the unreceived

Arm/Group Information *

There are three groups in the study.

Arm/Group Title *

Women intervention group= Group A

Couple intervention group= Group B

Controlled group= Group C

Arm/Group Description *§

Women intervention group: Only women will be intervened by Cognitive progressive muscular relaxation therapy.

Couple intervention group: Both couple will be intervened by Cognitive progressive muscular relaxation therapy.

Controlled routine activity group will have routine nursing care delivered by nurses.

Period(s) *

There is only one stage in the study.

Period Title *

Overall Study.

Started *

There will be 138 participants initiating the intervention.

Those 138 participants will be randomly assigned to three groups with around 46 participants in each group.

Completed *

We will do follow-up, and the number in the follow-up will be recorded.

Milestone Title [*]

Before the intervention, we will measure the participants, and the stage is defined as T0.

We will do follow-up immediately after intervention, defined as T1.

Reason Not Completed Type [*]

We will record the exact reason (Adverse Event) why participants do not complete the study. The reason may be death, lack of efficacy, lost to follow-up, illness, withdrawal by subject or others.

2. Baseline Characteristics

Arm/Group Information *

Chi-square test will be applied to figure out the difference of enumeration data among three groups. ANOVA will be applied to test the difference of measurement data among three groups. F values and χ^2 values will be displayed to show the baseline data are no different in three groups.

Arm/Group Title *

Women intervention group= Group A

Couple intervention group= Group B

Controlled group= Group C

Arm/Group Description *§

All the recruited participants will be numbered and randomly allocated into three groups by random number table. The grouping results will be announced to the participants according to the random number table.

Overall Number of Baseline Participants *

There will be 138 participants initiating the intervention.

Baseline Measure Information *

A group of demographic characteristics will be measured in the study, including gender, age, marital status, income per month, etc.

Baseline Measure Title *

- Age * : Continuous(years)
- Gender * : Female, Male
- Years after diagnosed with infertility: Continuous(years)
- Income per month: Categorical:
 - <=1000 RMB
 - >1000 and <2000 RMB
 - >=2000 RMB
- Educational level: Categorical:
 - Junior high school
 - Senior high school
 - College and above

Measure Type *

- Count of Participants: Gender
- Mean: Age, Years after diagnosed with infertility
- Number: Income per month, Educational level

Measure of Dispersion *

- Standard Deviation
- Inter-Quartile Range
- Full Range

Baseline Measure Data *

The value(s) for each baseline measure, for each group and overall cannot obtain right now since the study has not been started.

3. Outcome Measures

Outcome Measure Information *

A questionnaire will be used during each measurement, including several scales in it.

Dehydroepiandrosterone will also be tested.

Outcome Measure Type *

- Primary and secondary

Outcome Measure Title *

- Depression: depressive mood in recent two weeks measured by Zung Self-rated Depression Scale (SDS). It is a self-reported scale by adding up 20 items and the total score ranges from 20-80, with higher score reflects higher depression.
- Anxiety: Anxiety in recent two weeks measured by Zung Self-rated Depression Scale (SAS). It is a self-reported scale by adding up 20 items and the total score ranges from 20-80, with higher score reflects higher anxiety.
- Sleeping quality: a reflection of one's mood in recent month measured by Pittsburgh sleep quality index(PSQI). It is a self-reported scale, with total score higher than 19 reflects sleeping disorder. The differences within each time frames are the changes of sleeping quality
- Concentration of dehydroepiandrosterone in blood: a kind of hormone that reflects the

person's psychological stress.

- Success of IVF-ET: we will follow up the success of the participants of each group.

Outcome Measure unit *

The depression, anxiety, and sleeping quality are measured by scales with no unit.

Dehydroepiandrosterone has its concentration unit of pg/ml.

Outcome Measure Time Frame *

There will be two measurements, before the intervention and immediately after intervention.

They are defined as T0, T1.

Analysis Population Information

Overall Number of Participants Analyzed *

There will be 150 participants totally enrolled in the study.

Outcome Measure Data Table

Measure Type *

- Mean

Measure of Dispersion/Precision *

- Standard Deviation

Outcome Data *

The measurement value(s) for each outcome measure cannot obtain right now since the study has not been started.

Statistical Analysis Overview

Comparison Group Selection [*]

We will compare three groups' data.

Type of Statistical Test [*]

- Superiority
- Other (descriptive analysis)

P-Value [*]

P-Value will be set at 0.05.

Method [*]

- ANOVA
- Chi-Squared
- t-Test, 2-Sided
- Other: repeated measurement of variance analysis within different measurements among different groups

Estimation Parameter [*]

- Mean Difference (Final Values)

4. Adverse Event Information

Time Frame *§

The intervention lasts around 30 days, with 6 times, and we will record the adverse event at each time.

Adverse Event Reporting Description [*]

We will add relevant information about adverse event after finishing the study.

Collection Approach for Table Default *§

- Systematic Assessment: The psychotherapist will routinely determine whether or not certain adverse events have occurred through regular investigator assessment during intervention and in each follow-up.
- Non-Systematic Assessment: Self-reporting by participants or occasional assessment by the psychotherapist.

Adverse Event Term *

The most possible adverse event may be the psychological discomfort because the participants.

We will provide information for in three tables summarizing adverse events in each group,

including all-cause mortality, serious adverse events, and other (not including serious) adverse events.

Organ System *

- Psychiatric Disorders

5. Limitations and Caveats

The measurements are mostly based on self-reported scales and may lead to unreliable data. We will give instruction before fulfilling the questionnaire to ensure the participants understood.

6. Certain Agreements

Are all PIs Employees of Sponsor? *

- No: The principal investigator is not an employee of the sponsor

There is no agreement between the agent (university) and the principal investigators. The principal investigators are graduate students in the university. The principal investigators (PIs) can discuss the results of the study at a scientific meeting or any other public or private forum, or to publish in a scientific or academic journal information concerning the results of the study.

7. Results Point of Contact

Name or Official Title *

Professor: [name]

Position title: Director of Nursing Psychology Research Center

Organization Name *

Nursing Psychology Research Center, Xiangya School of Nursing, Central South University

Phone: *§

[name]

Email: *§ [contact]

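### Baseline ANOVA and chi-square tests cannot show that the three randomised groups are no different, so the planned comparability statement would be unsupported

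*Combined protocol and SAP*

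**What the plan says.** Section 2 (Baseline Characteristics, Arm/Group Information) sets out the baseline comparison. For categorical variables, "Chi-square test will be applied to figure out the difference of enumeration data among three groups"; for continuous variables, "ANOVA will be applied to test the difference of measurement data among three groups". The stated purpose is that the resulting F and chi-square values "will be displayed to show the baseline data are no different in three groups". No equivalence margin or standardised-difference criterion is given.

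The same section says that "All the recruited participants will be numbered and randomly allocated into three groups by random number table". The itemised baseline measures are age, gender, years since the infertility diagnosis, monthly income and education. Marital status is named in the text just before that list, which is left open-ended. The T0 values of SDS, SAS, PSQI and dehydroepiandrosterone (DHEA) are not itemised, although Sections 1 and 3 plan a measurement at T0.

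Section 3 (Outcome Measures) lists ANOVA, chi-square, a two-sided t-test and a repeated-measures analysis of variance. It names the estimation parameter as "Mean Difference (Final Values" (closing bracket omitted here). No ANCOVA or other covariate-adjusted model appears.

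**The concern.** The plan fixes its conclusion about baseline before any data exist and names a difference test as the proof. There are two separate faults. First, failing to reject a null of no difference does not establish that there is none. Second, in a properly randomised trial the groups are samples from one population, so the null is already known to be true and the test answers no open question. What matters is how far chance has separated the groups on variables that predict outcome, and a p-value does not measure that.

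At stake is what readers are told. A report that follows the plan would assert comparability on grounds that cannot carry it, next to final-value differences for which no baseline adjustment is specified. Running several such tests also makes an occasional spurious difference likely, and the plan does not say how one would be handled.

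**Working it through.** **Inputs.**
- Group size: Section 1 says "Those 138 participants will be randomly assigned to three groups with around 46 participants in each group". 3 × 46 = 138, which agrees with the stated total. The plan gives no sample-size derivation to reproduce.
- Level: Section 3 says "P-Value will be set at 0.05". I take this to cover the baseline tests.
- Number of baseline tests: five itemised measures, or six with marital status.
- Correlation r between T0 and T1 scores: not in the documents. Assumed 0.3, 0.5 and 0.7, with equal variance at both times.

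**1. Largest gap that stays non-significant.** With three groups of 46, the critical F on 2 and 135 df is 3.063. Let g be the highest-to-lowest gap in observed means, in within-group SDs.
- Third group midway: F = 46g²/4, so g = √(4 × 3.063/46) = 0.516.
- Third group equal to one of the other two: F = 46g²/3, so g = √(3 × 3.063/46) = 0.447.

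A gap below 0.447 SD is therefore never significant, and one between 0.447 and 0.516 SD may or may not be, depending on the third group. Section 3 also gives a total of 150. At 50 per group these limits scale by √(46/50) = 0.959, to about 0.43 and 0.49 SD (treating the critical value as unchanged).

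**2. What passing the test leaves behind.** In 200,000 simulated null allocations at 46 per group, 95% gave a non-significant F. Among those, the highest-to-lowest gap was at least 0.3 SD in about 28% and at least 0.4 SD in 9%. The median gap was 0.23 SD.

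**3. False alarms.** With k independent tests at 0.05 and no true differences, the chance of at least one p < 0.05 is 1 − 0.95^k:
- k = 5: 1 − 0.95⁵ = 0.226
- k = 6: 1 − 0.95⁶ = 0.265

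Independence is an assumption; income and education, for example, are probably related.

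**4. What a passing gap could do to an outcome comparison.** Take two groups whose T0 scores differ by d SD through chance, and compare final values unadjusted. The standard error is √(2/46) = 0.2085 SD and the critical difference is 1.96 × 0.2085 = 0.409 SD. Given d and no treatment effect, the expected final-value difference is r × d, with standard error √(1 − r²) × 0.2085.

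Example with r = 0.5 and d = 0.4: shift 0.20, standard error 0.1806, (0.409 − 0.20)/0.1806 = 1.16. The conditional type I error is 0.124.

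| r | d = 0.3 | d = 0.4 |
|---|---|---|
| 0.3 | 6.1% | 7.7% |
| 0.5 | 7.7% | 12.4% |
| 0.7 | 9.1% | 19.4% |

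If d is the highest-to-lowest gap, both values lie below 0.447, so the F-test would not flag them. Averaged over all randomisations the error rate stays at 5%.

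**5. The repeated-measures analysis.** With two time points its group-by-time test is a comparison of change scores. Given d, the expected difference in change is (r − 1) × d. At r = 0.5 and d = 0.4 this is −0.20, the same size as the final-value shift with the opposite sign. Relative to the unadjusted final-value comparison, variance is multiplied as follows at r = 0.3, 0.5 and 0.7:
- Change score, 2(1 − r): 1.4, 1.0, 0.6
- ANCOVA, 1 − r²: 0.91, 0.75, 0.51

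**6. Gain from adjustment.** The pairwise difference detectable with 80% power is (1.96 + 0.842) × 0.2085 = 0.58 SD unadjusted. Multiplied by √(1 − r²), it becomes 0.56, 0.51 and 0.42 SD under ANCOVA.

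**The case against.** The strongest reply is that this concerns reporting only: the sentence changes no planned outcome test or estimate, and randomisation protects the comparison however baseline is described. Much of that stands, and it rules out several stronger readings.

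- **That the comparability statement would be false.** It would be unsupported. On a given variable, about 72% of passing allocations have no gap as large as 0.3 SD, so the groups may well be close.
- **That the baseline tests license the unadjusted outcome analysis.** No section links the two. The plan also lists no covariate model, so choosing covariates after seeing imbalance is a possibility, not something it provides for.
- **That the outcome analysis ignores T0.** The repeated-measures analysis in Section 3 uses it. It is not ANCOVA, however, the named estimate is still the final-value difference, and the plan does not say which method governs.
- **That the fault is low power at 46 per group.** Power to detect a given baseline difference presupposes a population difference, which proper randomisation excludes. More participants would not make the test useful.
- **That the T0 scores are certainly left out of the baseline table.** The list is open-ended and those scores are collected. The plan simply does not say that they will be shown.

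What the reply does not answer is that the plan states an inference, in terms, that the named tests cannot deliver.

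**Conclusion.** The point holds as a minor to moderate fault, wrong as written. The logical objection needs no assumption beyond properly conducted randomisation. The gap limits and the 28% figure assume 46 analysed units per group and, for the simulation, normally distributed values. The plan does not say whether the 46 are couples or individuals, and its totals of 138 and 150 need reconciling; 50 per group would not change the conclusion. The 23% to 26% false-alarm figure assumes independent tests. The conditional error rates of about 6% to 19% rest on assumed correlations and on a chance gap of 0.3 to 0.4 SD having occurred. They illustrate conditional bias and do not show that the planned comparisons are invalid on average.

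**What to change.** In Section 2, delete the baseline ANOVA and chi-square tests and the sentence stating what they will show. Suggested replacement:

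*Baseline variables, including T0 SDS, SAS, PSQI and DHEA, will be summarised by group as mean (SD) or number (%), without significance tests. No conclusion that the groups are equal will be drawn from a p-value.*

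Deleting the tests alone would leave the final-value comparison unadjusted, so add to Section 3:

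*For SDS, SAS, PSQI and DHEA, the between-group difference in final values will be estimated by ANCOVA with the T0 value of the same outcome as covariate, whatever baseline balance is observed.*

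IVF-ET success has no T0 value and is outside this addition. The cost is a wording change and a simpler baseline table. No new data are needed, because the T0 measurements are already planned.

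### Age and years since diagnosis are collected but enter no outcome analysis; adjusting the IVF-ET success comparison for them is a cheap gain in precision, not the repair of an invalid test

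*Combined protocol and SAP*

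**What the plan says.** All references are to the combined protocol and SAP.

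- **Outcome.** Section 3, Outcome Measure Title, ends its list with "Success of IVF-ET: we will follow up the success of the participants of each group". It gives no definition of success, no time point, no unit of analysis and no named test.
- **Covariates held.** Section 2, Baseline Measure Title, lists "Age * : Continuous(years" and "Years after diagnosed with infertility: Continuous(years" among the baseline measures.
- **Their use.** Apart from description, the only stated use is a between-group test at baseline: "ANOVA will be applied to test the difference of measurement data among three groups". The stated aim is that "F values and χ^2 values will be displayed to show the baseline data are no different in three groups". No action follows from the result.
- **Allocation.** Participants are "randomly allocated into three groups by random number table" (Section 2, Arm/Group Description). No stratification or minimisation is stated.
- **Outcome methods.** Section 3, Method, lists ANOVA, chi-square, a two-sided t-test and repeated-measures ANOVA, without matching any of them to an outcome. No covariate, regression model or stratified test appears. The only estimation parameter is a difference in final means.
- **Size.** Section 1: "Those 138 participants will be randomly assigned to three groups with around 46 participants in each group". Section 3, under the number analysed, has instead "There will be 150 participants totally enrolled in the study".

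**The concern.** The questionnaire scores and the hormone level have a T0 value that can serve as a baseline. IVF-ET success cannot have one, so age and years since diagnosis are the natural baseline information for it that the trial already holds. Neither the allocation nor the analysis uses them.

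If they predict success, two things follow. Whatever chance imbalance occurs in this one trial stays in the observed success difference, where it can add to or mask an effect of the therapy. The comparison is also somewhat less precise than the data allow. Precision is scarce here: at 46 per group, power is only about 48-50% for a 20-point difference in success, for control rates of 30% to 50%.

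**Working it through.** The plan states no power, effect size, SD or success rate, so it has no figure to reproduce; 3 × 46 = 138 agrees as arithmetic only.

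**Inputs.** From the documents: 46 per group and a 0.05 level. Assumed: one record per couple, age SD 4.5 years, success 40%, log-odds of success falling 0.05 to 0.15 per year of age.

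**1. Chance age gap between two groups**
- Standard error: 4.5 × √(2/46) = 0.94 years.
- Median absolute gap: 0.674 × 0.94 = 0.63 years.
- 95% limit: 1.96 × 0.94 = 1.84 years, or 1.84/4.5 = 0.41 SD.

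**2. Shift in the success difference with no therapy effect** (slope × gap × 0.4 × 0.6)
- Median gap: 0.05 × 0.63 × 0.24 = 0.8 points, to 0.15 × 0.63 × 0.24 = 2.3 points.
- 95%-limit gap: log-odds shift 0.092 to 0.276 (odds ratio 1.10 to 1.32); times 0.24, this is 2.2 to 6.6 points.
- Sampling standard error of the difference: √(2 × 0.24/46) = 10.2 points.

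With 150 participants (50 per group) little changes: the gap limit is 1.96 × 4.5 × √(2/50) = 1.76 years, the shift 2.1 to 6.4 points and the standard error √(0.48/50) = 9.8 points.

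**3. Cross-check per SD.** The slopes correspond to odds ratios per SD of e^(0.05 × 4.5) = 1.25 and e^(0.15 × 4.5) = 1.96. Integrating a logistic model over the covariate at 40% success, a 0.4 SD gap gives a spurious difference of 2.1 points (odds ratio 1.25) to 6.0 points (odds ratio 2.0). Given that gap, the rejection rate for that pair under no effect is 5.5% to 9.1%. A gap above 0.4 SD has a 5.5% chance for one named pair and about 13% for at least one of the three pairs.

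**4. Would the baseline ANOVA reveal it?** With the third group midway, F = 46 × (d²/2)/2 on 2 and 135 degrees of freedom.
- d = 0.3 SD: p about 0.36.
- d = 0.4 SD: p about 0.16.
- d = 0.5 SD: p about 0.06.

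A gap at the 95% limit would be reported as no difference.

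**5. Three-group test over repeated randomisations.** Simulation: 3,000 trials per setting, 46 per group, 40% success, two independent covariates of equal strength. The unadjusted test is the chi-square; the adjusted test is the logistic likelihood-ratio test. For power, both active groups have a log odds ratio of 1.0 against control.

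| Odds ratio per SD | Null rejection, unadjusted / adjusted | Power, unadjusted / adjusted | Gain (points) |
|---|---|---|---|
| 1.25 | 4.7% / 5.1% | 67.4% / 68.7% | 1.3 |
| 1.5 | 4.8% / 5.5% | 61.9% / 66.1% | 4.2 |
| 2.0 | 4.9% / 5.4% | 50.8% / 59.9% | 9.1 |

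The first gain reads as 2 points if the percentages are rounded before subtraction. Part of each gain reflects the slightly liberal adjusted test. A two-group simulation (46 vs 46, 35% vs 60% success) gave power of 66-69% unadjusted and 68-74% adjusted, with null rejection of 4.9-5.9% for the adjusted test.

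**6. Cost if the covariates predict nothing.** By the linear-model approximation, two useless covariates inflate the variance by 1 + 2/(135 − 2 − 1) = 1.015. The two-group simulation gave an unadjusted-to-adjusted variance ratio of 0.98 with weak covariates and up to 1.09 with stronger ones. The loss is therefore about 2%.

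**The case against.** The strongest reply is that nothing here is an error. Allocation is random, and the 5% level of the chi-square already allows for chance imbalance; step 5 shows 4.7-4.9%. This stands. A reader might infer that the unadjusted comparison is biased or has an inflated false-positive rate. The documents do not support that: the raised rates in step 3 hold only given that a particular imbalance has occurred.

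The size is also modest. The 2 to 7 points belong to a gap at the 95% limit. The median gap gives 1 to 2 points, and even the upper figure is below one sampling standard error. This stands too, as does the point that the documents say nothing about how strongly age or duration predicts success.

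The plan does not actually assign the chi-square to success. That is correct. It is an inference from the type of outcome, and the only listed method that fits.

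Finally, a covariate model cannot be written until success, the unit of analysis and whose age counts are settled. Section 2 lists age beside a gender item with both categories, so the records may include men, and two partners share one IVF-ET result. This is a fair limit on the remedy and is built into it below. None of these replies gives a reason to leave the covariates unused.

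**Conclusion.** The point holds as a recommended improvement, not as a defect of validity. Two variables already collected enter no outcome analysis, and the only suitable listed test for IVF-ET success ignores them. The cost is some lost precision and an uncorrected chance imbalance in the trial actually run.

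Under the stated assumptions the shift is typically 1 to 2 points, and 2 to 7 at the 95% limit, against a standard error of about 10. The power gain runs from about 1 point with weak covariates to about 9 when both have an odds ratio of 2.0 per SD. These sizes rest on assumed SD, success rate and slopes, on independent covariates and on 46 couples per group. If the 138 counts individuals and partners are separate rows, there are fewer independent IVF-ET results and the noise is larger.

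It would also be too strong to infer that adjustment removes the imbalance. It reduces it only as far as the model form holds, and only for the covariates in the model.

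**What to change.** First define IVF-ET success and when it is assessed, and state that the unit is one record per couple (the woman). Then pre-specify, to be applied whatever the baseline p-values show:

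- a logistic model for success with group, the woman's age and years since infertility diagnosis, both covariates continuous;
- covariate-standardised risk differences for A−C, B−C and B−A with 95% confidence intervals, which stay on the same scale as the raw proportions;
- the unadjusted chi-square and raw proportions as a supporting table.

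Fix this before outcome data are seen, so that covariates are not chosen in the light of the results.

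The cost is SAP wording, plus a check that the woman's age is recorded for every couple. Statistically it takes two extra parameters, a precision loss of about 2% if neither covariate is prognostic, and a slightly liberal likelihood-ratio test at this size (null rejection about 5-6%). The conflict between 138 and 150 participants should be reconciled as well, though this point does not depend on it.

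### The planned sample size is inconsistent: 138 enrolled, randomised and started in sections 1 and 2, but 150 enrolled in section 3

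*Combined protocol and SAP*

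**What the plan says.** **Section 1, Participant Flow.** The flow table puts anticipated total enrolment at 138 and allocates 46 to each of groups A, B and C. Under *Started* the text gives 138 as the number beginning the intervention and continues: "Those 138 participants will be randomly assigned to three groups with around 46 participants in each group". Under *Pre-assignment Details* the order of events is an eligibility check, then a settled list of enrolled participants, then randomisation: "We firstly will assess the recruited people to ensure meeting the inclusion and exclusion criteria".

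**Section 2, Baseline Characteristics.** Under *Overall Number of Baseline Participants*: "There will be 138 participants initiating the intervention".

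**Section 3, Outcome Measures.** Under *Analysis Population Information*, *Overall Number of Participants Analyzed*: "There will be 150 participants totally enrolled in the study".

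The number at follow-up is left open, to be counted when it is known: "We will do follow-up, and the number in the follow-up will be recorded".

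**The concern.** Sections 1 and 3 both give a figure for total enrolment, and the figures differ. The document carries a single date and has no amendment log. The sentence with 150 is complete, so neither a redaction nor a broken table accounts for it.

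A reader working from section 1 would stop recruiting at 138, and one working from section 3 would stop at 150. The plan gives no power, effect size, standard deviation or loss rate, so neither total can be derived and the reader cannot tell from a calculation which was meant.

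The entry also fails at its own job. It sits where the size of the analysed population should be, but it gives an enrolment figure, and that figure exceeds the number to be randomised.

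**Working it through.** **Inputs**

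| Quantity | Value | Place |
|---|---|---|
| Anticipated total enrolment | 138 | Section 1, flow table |
| Allocation | 46 / 46 / 46 | Section 1, flow table |
| Number starting and randomised | 138 | Section 1, *Started* |
| Baseline number | 138 | Section 2, *Overall Number of Baseline Participants* |
| Total enrolled | 150 | Section 3, *Overall Number of Participants Analyzed* |
| Alpha, sidedness of t-test | 0.05, two-sided | Section 3, *P-Value* and *Method* |
| Power | 80% (assumed; not in the document) | – |

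**Step 1. Reproduce the plan's figure.** 3 × 46 = 138. This agrees exactly with the enrolment, randomisation, starting and baseline figures.

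**Step 2. Test 150 against the same allocation.** 150 / 3 = 50 per group, a group size that appears nowhere. The gap is 150 − 138 = 12 in total, or 50 − 46 = 4 per group. As a share, 12 / 138 = 8.7% and 12 / 150 = 8.0%.

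**Step 3. Try the explanations that could link the two numbers.**

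- *150 enrolled, 138 left after loss.* Inflating 138 by 1 / (1 − d), rounded up, gives 146 at d = 5%, 150 at d = 8%, 154 at d = 10% and 173 at d = 20%. Only a rate of about 8% links the figures, and no rate is stated. Section 1 also gives 138 as the number enrolled, randomised and starting, so it is not a count after loss from the study.
- *Couples against individuals.* 138 couples would be 2 × 138 = 276 people, not 150.
- *150 analysed.* Impossible if 138 are randomised.
- *150 recruited before the eligibility check.* Taken up under the objection.

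**Step 4. Size of the effect on precision.** This takes a two-sample t-test with equal groups, two-sided alpha 0.05, assumed power 80%, independent participants and no adjustment for multiple comparisons.

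- Smallest detectable difference: 0.590 SD at 46 per group and 0.566 SD at 50.
- Standard-error ratio: √(46/50) = 0.959, so 4.1% smaller at 50.
- Power at 50 per group for a difference of 0.590 SD: 0.832, against 0.80 at 46.
- With a Bonferroni adjustment for three pairs (also an assumption): 0.69 and 0.66 SD.

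The normal approximation, (1.96 + 0.84) × √(2/n), gives 0.58 and 0.56 SD and leads to the same conclusion.

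**The case against.** The strongest defence is that 150 is a gross recruitment count and 138 is what remains after the eligibility check. The wording on recruitment is loose enough to allow it. Section 1 applies the term recruited to people not yet checked for eligibility, whereas section 2 uses it for those who are randomised: "All the recruited participants will be numbered and randomly allocated into three groups by random number table". The enrolment row of the flow table also carries an instruction that mixes the two stages: "Record the number of the eligible and the excluded". This reading is not ruled out, but it is weak. That same row gives 138, section 1 settles enrolment after the eligibility check, and section 3 says enrolled, not recruited or screened. Even if it were right, the figure would be under the wrong heading and would still clash with the enrolment entry in the flow table.

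A second defence is that little depends on the number. This largely stands. Four entries agree on 138 and one sentence differs, and no stated test, alpha or outcome depends on 150. Nothing is miscalculated either: 3 × 46 = 138 is correct, so this is an inconsistent figure and not an arithmetic error.

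Two stronger readings are tempting, and the document supports neither.

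- A reader might infer that the plan intends to analyse 150 people. Only the heading suggests it; the sentence speaks of enrolment.
- A reader might infer that attrition could not be worked out at the end. Section 1 provides for recording counts at enrolment, allocation and follow-up, so losses can still be computed on the number actually randomised.

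**Conclusion.** The point holds as a minor internal inconsistency, wrong as written. The document gives two totals for planned enrolment, 138 and 150, and does not explain the difference of 12 (8.7% of 138). The weight of the text is on 138, the only figure that fits the allocation table, but the document does not exclude that the sponsor had 150 in mind.

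The contradiction needs no assumption; it follows from reading the entries together. The precision figures do rest on assumptions: 80% power, independent participants and unadjusted pairwise comparisons. Independence is uncertain, because group B treats both partners, gender is recorded as female or male, and it is not clear whether 46 counts individuals or couples. The figures serve only to show that the choice between 46 and 50 per group changes little. A reader might conclude that the trial is underpowered at 138, but without a stated target effect or power that does not follow.

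**What to change.** Replace the sentence with 150 in section 3 by: *The planned number enrolled and randomised is 138 (46 per group).* This agrees with the flow table, the *Started* sentences and the baseline number. It costs one sentence and adds no participants.

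If the sponsor did intend 150, it should say which count that is and align the rest:

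- *150 recruited, 138 randomised:* label 150 as recruitment, make the enrolment row of the flow table agree, and state the assumed loss before randomisation. This means 12 more people recruited and none added to the randomised groups.
- *150 randomised:* change the flow table and the *Started* sentences in section 1 and the baseline number in section 2. This means 12 more participants, 4 per group.

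Under *Overall Number of Participants Analyzed*, state that the number analysed will be reported separately for each group and each outcome. The correction should not bring in a rule limiting analysis to participants with T1 data. The document contains no such rule, reconciling two counts does not need one, and it could exclude randomised participants. It would also not suit the IVF-ET success outcome, which the document does not make conditional on having T1 data.
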